### **3.1.3 Neurological Assessment Study**

A focused neuropathological evaluation will be integrated within the Main Study. This subset of subjects will be included in the neurological assessment evaluable subgroup (NAE). Subjects will be assessed for incidences of symptomatic and asymptomatic pre-and post-ablation cerebral emboli with either an absence of CNS deficits (asymptomatic) or with emboli-associated neurological symptoms (symptomatic).

A prospective evaluation of 40 subjects at participating sites will be included in this assessment. The mandatory roll-in subjects will not be eligible for the NAE assessment to minimize the confounding influence of a learning curve during early use of a complex medical device. Enrollment in the NAE population may be terminated prior to achieving the target 40 subjects if study enrollment ends early after a planned interim look.

At participating sites and considering the above caveats, all subjects (non roll-in) who are enrolled in the main study will be considered for participation in the NAE, per specific eligibility requirements:

1. IF a subject satisfies any one of the 3 following conditions he/she will be excluded from the NAE:
  - Presence of iron-containing metal fragments in the body
  - Subject has a contraindication to use of contrast agents for MRI such as advanced renal disease etc. (at PI discretion)
  - Subject has an unresolved pre-existing neurological deficit.
2. Subject must provide written informed consent for MRI, NIHSS, MoCA, mRS, and general neurological assessments.

## 3.2 Study Endpoints

### 3.2.1 Primary Endpoints

- **Acute Safety**

The primary safety endpoint is the incidence of early onset Primary Adverse Events (PAEs) (within seven (7) days of the initial mapping and ablation procedure). PAEs include the following AEs (refer to Section 9.1.3 for a complete list and definitions):

Death*	Stroke/CVA
Atrio-Esophageal Fistula*	TIA
Myocardial Infarction	Phrenic Nerve Paralysis
Cardiac Tamponade/perforation	Pulmonary Vein Stenosis*
Thromboembolism	Major Vascular Access Complication/Bleeding

\* Device or procedure related death, pulmonary vein stenosis and atrio-esophageal fistula that occur greater than one week (7 days) and ( $\leq$ ) less or equal to 90 days post-procedure are considered and analyzed as primary AEs.

- **Acute Effectiveness**

Acute procedural success defined as confirmation of entrance block in treated PVs after adenosine and/or isoproterenol challenge (with or without the use of a focal catheter)

### 3.2.2 Secondary Endpoints

- **Safety:**

- incidence of individual PAE from the primary composite
- Incidence of Serious Adverse Device Effects (SADEs)
- Incidence of Serious Adverse Events (SAEs) within 7 days (early onset), >7-30 days (peri-procedural) and >30 days (late onset) of initial ablation procedure
- Incidence of non-serious adverse events
- Incidence of pre-and post-ablation asymptomatic and symptomatic cerebral emboli as determined by MRI evaluations.
- Frequency, anatomic location, and size (diameter and volume) of cerebral emboli by MRI evaluations at baseline, post-ablation and during follow-up.
- Incidence of new or worsening neurologic deficits, post-ablation and at follow-up, compared to baseline.
- Summary of NIHSS scores at baseline, post-ablation and during follow-up.

- Summary of MoCA scores at baseline, 1 month follow-up and during further follow-up.
- Hospitalization for cardiovascular events (with hospitalization defined as prolonged stay  $\geq 2$  nights post index procedure or in-patient stay not concurrent with index procedure  $\geq 1$  calendar day)
- **Effectiveness:**
  - Percentage (%) of PVI touch-up by focal catheter among all targeted veins and by subject.
  - Percentage (%) of subjects with use of focal catheter ablation for non-PV triggers
  - Percentage (%) of subjects with freedom from documented, symptomatic atrial fibrillation (AF), atrial tachycardia (AT), or atypical (left side) atrial flutter (AFL) episodes (episodes  $>30$  seconds on arrhythmia monitoring device from day 91 to 180).
  - Percentage (%) of subjects with freedom from documented, atrial fibrillation (AF), atrial tachycardia (AT), or atypical (left side) atrial flutter (AFL) episodes (episodes  $>30$  seconds on arrhythmia monitoring device from day 91 to 180).
  - Percentage (%) of subjects with freedom from documented, symptomatic atrial fibrillation (AF), atrial tachycardia (AT), or atypical (left side) atrial flutter (AFL) episodes (episodes  $>30$  seconds on arrhythmia monitoring device from day 91 to 365).
  - Percentage (%) of subjects with freedom from documented, atrial fibrillation (AF), atrial tachycardia (AT), or atypical (left side) atrial flutter (AFL) episodes (episodes  $>30$  seconds on arrhythmia monitoring device from day 91 to 365).
- **Additional analyses on procedural characteristics, including but not limited to:**
  - Total procedure time, ablation time, RF application time, balloon dwell time, time to effect (PVI)
  - Number and time of RF applications per PV location
  - Fluoroscopy time and dose
- **Health economic assessments, including but not limited to:**
  - Index procedural workflow costs
  - Hospital costs
  - Quality of Life (AFEQT questionnaire)

Roll-in subjects will not be included in the main study analyses and will be analyzed separately.

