**Main Secondary Endpoints:**

- Incidence of individual PAE from the primary composite
- Incidence of Serious Adverse Device Effects (SADEs)
- Incidence of Serious Adverse Events (SAEs) within 7 days (early-onset), >7-30 days (peri-procedural) and >30 days (late onset) of initial ablation procedure
- Incidence of non-serious adverse events
- Incidence of pre-and post-ablation asymptomatic and symptomatic cerebral emboli as determined by MRI evaluations.
- Frequency, anatomic location, and size (diameter and volume) of cerebral emboli by MRI evaluations at baseline, post-ablation and during follow-up.
- Incidence of new or worsening neurologic deficits post-ablation and follow-up, compared to baseline.
- Summary of NIHSS scores at baseline, post-ablation and during follow-up.
- Summary of MoCA and mRS scores at baseline, 1 month and during further follow-up.
- Hospitalization for cardiovascular events
- Percentage (%) of PVI touch-up by focal catheter among all targeted veins and by subject.
- Percentage (%) of subjects with use of focal catheter ablations for non-PV triggers.
- Percentage (%) of subjects with freedom from documented symptomatic atrial fibrillation (AF), atrial tachycardia (AT), or atypical (left side) atrial flutter (AFL) episodes (episodes >30 seconds on arrhythmia monitoring device from day 91 to 180).
- Percentage (%) of subjects with freedom from documented atrial fibrillation (AF), atrial tachycardia (AT), or atypical (left side) atrial flutter (AFL) episodes (episodes >30 seconds on arrhythmia monitoring device from day 91 to 180).
- Percentage (%) of subjects with freedom from documented symptomatic atrial fibrillation (AF), atrial tachycardia (AT), or atypical (left side) atrial flutter (AFL) episodes (episodes >30 seconds on arrhythmia monitoring device from day 91 to 365).
- Percentage (%) of subjects with freedom from documented atrial fibrillation (AF), atrial tachycardia (AT), or atypical (left side) atrial flutter (AFL) episodes (episodes >30 seconds on arrhythmia monitoring device from day 91 to 365).
- Procedural parameters including but not limited to: total procedure and ablation time, balloon dwell time, RF application time, time to effect (PVI measured by Frontera), number of RF applications, fluoroscopy time and dose.
- Health economic data, including but not limited to index procedural workflow costs, QoL and hospital costs.

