- Prior to ablation in the region of the right sided veins, precautionary measures to evaluate the proximity to the phrenic nerve are mandatory.
  - Pace out of the superior vena cava (SVC) for phrenic nerve pacing.
  - Assure diaphragmatic capture PRIOR to RF delivery.
  - Stop RF delivery if phrenic nerve capturing is lost or attenuated.
- Ensure continuous monitoring of ablation parameters, PV recordings and esophageal temperature during RF energy delivery.
  - Stop RF ablation posteriorly if esophageal temperature rises more than 2 degrees from baseline temperature.
  - Record time to Pulmonary Vein Isolation. Bonus lesions are not permitted once acute PVI has been confirmed
  - Turn off RF energy delivery to posterior electrodes after maximum 20 seconds
- All subjects will undergo PV ablation with the Balloon Catheter until PVI is achieved and isolation confirmed by Frontera Catheter
- Confirmation of entrance block of all targeted PV by Frontera Catheter
- Additionally, in case of roll-in subjects, confirm entrance block of all targeted PV with Lasso® and perform voltage mapping
- Administer adenosine or isoproterenol for each targeted PV to rule out dormant conduction.
- (If necessary and at the investigator's discretion, a commercially available ThermoCool® family catheter may be inserted to complete PVI or other identified targets.)
- Confirmation of entrance block of all targeted PVs

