##### **RF ablation parameters per PV**

- Number of RF application(s) per target PV
- Number of RF application(s) required with a focal catheter
- Total RF duration per target PV
- Total time of RF application with the balloon catheter until PV isolation of targeted vein was achieved (TTI = time to isolate)
- Total time of RF application with the focal catheter (if applicable)
- PVI confirmed with Frontera Catheter
- PVI confirmed with Lasso® (roll-in subjects only)
- PV acute reconnection yes/no

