11 STATISTICAL ANALYSIS METHODS

11.1 General Conventions

Standard descriptive summaries for continuous data will include the number of observations with data, mean, standard deviation, median, 25% percentile, 75% percentile, minimum, and maximum values. For categorical data, count and percentages of observations will be provided. Summaries will be based on subjects without missing data.

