11.6 Analysis of Procedural Data

Procedural data such as total procedure duration, fluoroscopy duration and dose, RF application time, balloon dwell time, time to effect (PVI), number and time of RF applications per PV location, fluid delivery, output and balance will be summarized with descriptive statistics. These analyses will be conducted using the PP population and the roll-in subjects.

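### Time to effect (PVI) has no rule for a vein the balloon never isolates; under the plan's only operational definition such veins would drop out, leaving a summary conditional on balloon success

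*Protocol*

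**What the plan says.** - **Endpoint.** Protocol 3.2.2 lists "Total procedure time, ablation time, RF application time, balloon dwell time, time to effect (PVI" under additional analyses of procedural characteristics. The Protocol Summary places it among the main secondary endpoints, as a procedural parameter, and names the measuring catheter: "time to effect (PVI measured by Frontera".
- **Procedure.** Protocol 8.2.2.3 expects balloon ablation to run to isolation: "All subjects will undergo PV ablation with the Balloon Catheter until PVI is achieved and isolation confirmed by Frontera Catheter". It instructs the site to "Record time to Pulmonary Vein Isolation". Drug challenge comes next, and after it the option that "a commercially available ThermoCool® family catheter may be inserted to complete PVI or other identified targets".
- **Data item.** Protocol 8.2.3.1 collects, per vein, "Total time of RF application with the balloon catheter until PV isolation of targeted vein was achieved (TTI = time to isolate". It also collects, per vein, focal applications, focal RF time, Frontera confirmation and acute reconnection. It does not say what to enter when the balloon does not isolate the vein.
- **Analysis.** SAP 11.6 covers "time to effect (PVI), number and time of RF applications per PV location" with descriptive statistics, in the PP population and the roll-in subjects. SAP 11.1 adds: "Summaries will be based on subjects without missing data".
- **Missing counts.** Protocol 14.8.1 includes the number of missing observations in the standard summary of continuous data. The list in SAP 11.1 does not.

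**The concern.** A time that is defined as ending at isolation exists only where isolation occurred. If the balloon never isolates a vein and the operator finishes with a focal catheter or stops, the item has no value. Complete-case descriptive statistics then leave the vein out. The veins lost this way are probably the difficult ones, so the loss is not neutral: as the balloon fails in more slow veins, more of the slow tail disappears, and the mean and median can stay the same or improve.

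The measure carries weight because the primary effectiveness endpoint counts success with or without a focal catheter, so it does not isolate balloon performance. Time to effect is one of the planned outcomes that does. Because SAP 11.1 does not list the missing count, a reader might not see how many veins the summary omits.

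**Working it through.** The plan gives no expected time, standard deviation or target for time to effect, so it has no figure to reproduce. The check has two parts.

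**1. Which veins can lack a time?** Taking the order of steps in Protocol 8.2.2.3:

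| Course of the vein | Balloon isolation time exists? |
|---|---|
| Isolated by balloon, stays isolated | Yes |
| Isolated by balloon, reconnects, focal touch-up | Yes, recorded before the touch-up |
| Never isolated by balloon, completed with focal catheter | No |
| Never isolated | No |

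Only the last two rows are affected. Call their share of targeted veins *f*.

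**2. How far would the summary move?** Let *T* be the balloon RF time a vein would need, with distribution function *F*. Assume that the never-isolated veins are the slowest fraction *f*.

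- All-vein percentile *p*: the time *t* with *F(t) = p*.
- Percentile *p* among isolated veins only: the time *t* with *F(t) = p(1 - f)*.
- Ratio of observed to all-vein value:
  - exponential *T*: ln(1 - p(1 - f)) / ln(1 - p)
  - lognormal *T*, log-SD 0.5: exp{0.5 [z(p(1 - f)) - z(p)]}, with *z* the standard normal quantile.

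Both distributions, the log-SD and the values of *f* are assumptions.

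Worked case, *p* = 0.5 and *f* = 0.05, so p(1 - f) = 0.475:
- exponential: ln(0.525) / ln(0.5) = 0.6444 / 0.6931 = 0.930
- lognormal: exp{0.5 × (-0.0627 - 0)} = 0.969

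| *f* | Median ratio, exponential | Median ratio, lognormal | 90th percentile ratio, exponential | 90th percentile ratio, lognormal |
|---|---|---|---|---|
| 0% | 1.000 | 1.000 | 1.000 | 1.000 |
| 1% | 0.986 | 0.994 | 0.963 | 0.975 |
| 2% | 0.971 | 0.988 | 0.928 | 0.953 |
| 5% | 0.930 | 0.969 | 0.839 | 0.894 |
| 10% | 0.862 | 0.939 | 0.721 | 0.817 |

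One result for the median does not depend on the distribution. As long as never-isolated veins count as longer than the median, the all-vein median is the 0.5/(1 - f) quantile of the observed times: the 51.0th percentile at 2%, the 52.6th at 5% and the 55.6th at 10%.

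**What is known about *f*.** The only figure in the documents is from the feasibility study (Protocol 1.2.3): all treated veins were isolated without a focal catheter. With 0 events in *V* veins, the one-sided 95% upper bound is 1 - 0.05^(1/V). The number of veins is not given. At an assumed 3, 4 or 5 veins in each of 39 subjects (117, 156 or 195 veins), the bound is 2.5%, 1.9% or 1.5%. This treats veins as independent, which they are not within a subject, so the true bound is somewhat higher.

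**The case against.** The strongest case against the point is that it completes the plan by inference. No section restricts time to effect to veins isolated by the balloon. None equates it with the TTI item in Protocol 8.2.3.1, and SAP 11.1 speaks of subjects, not veins. A vein finished with a focal catheter might instead be entered with its balloon RF time. That is right as a reading of the text, so the point is stated conditionally. It does not rescue the plan, because that alternative would record a balloon failure as a balloon isolation, and a vein never isolated would still have no value.

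A reader might also infer that every vein needing the focal catheter drops out. The documents do not support this. Focal use is listed after balloon isolation, Frontera confirmation and drug challenge, so a vein touched up after reconnection already has its time.

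It is also fair to say that related results stand beside this one. SAP 11.5.2.2 reports touch-up among all targeted veins, and SAP 11.6 reports the number and time of RF applications per vein location. A device that failed often would show it there. This limits the harm, but the touch-up percentage does not supply the missing denominator: it pools never-isolated veins with reconnected ones.

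Finally, the measure is descriptive, with no hypothesis or performance goal. That stands.

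**Conclusion.** The point holds as a gap in definition that, by default, would favour the device. Under the only operational definition and the complete-case convention, the summary would be conditional on balloon success and would understate time to isolation if any targeted vein is never isolated by the balloon.

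The median would be about 1-3% too low at 2% never isolated, 3-7% at 5% and 6-14% at 10%. The 90th percentile would be about 5-7%, 11-16% and 18-28% too low. These ranges rest on the two assumed distributions and on never-isolated veins being the slowest. At 0%, as in the feasibility study, there is no shift.

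It would go too far to conclude that the reported time will be too short: the documents give no non-zero share, and the feasibility result suggests a small one. Both primary tests, the error rates and the sample size are untouched. This is a cheap improvement to a descriptive procedural endpoint.

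**What to change.** In SAP 11.6:

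1. Define time to effect per targeted vein as balloon RF time to first isolation confirmed by the Frontera catheter.
2. Report the number of veins isolated by the balloon over the number targeted.
3. Show the cumulative percentage of all targeted veins isolated, against balloon RF time. Keep never-isolated veins in the denominator as not isolated to the end of the curve. Do not censor them when balloon RF stops, since that would assume they would have gone on to be isolated like the rest.
4. Read the median and upper percentiles from this curve, and state that a percentile is not reached where that is so.
5. Let veins that were isolated by the balloon and later reconnected keep their recorded time. Report reconnection and touch-up separately.
6. Label any mean among isolated veins as conditional on balloon isolation.

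The per-vein items in Protocol 8.2.3.1 already supply balloon RF time, focal use, Frontera confirmation and reconnection. It is worth confirming before database lock that a blank isolation time can be told apart from a time not recorded. The cost is SAP wording and one extra output. The small downside is that reported times may be slightly longer.

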## 4 Study Population

### 4.1 Participant Inclusion Criteria

Candidates for this study must meet ALL of the following criteria:

1. Diagnosed with Symptomatic Paroxysmal AF.
2. Selected for AF ablation procedure for pulmonary vein isolation.

3. Able and willing to comply with uninterrupted per-protocol anticoagulation requirements
4. Age 18-75 years
5. Able and willing to comply with all pre-, post- and follow-up testing and requirements.
6. Signed Patient Informed Consent Form.

## 4.2 Participant Exclusion Criteria

Candidates will be excluded if ANY of the following criteria apply:

1. AF secondary to electrolyte imbalance, thyroid disease, or reversible or non-cardiac cause.
2. Previous surgical or catheter ablation for AF.
3. Anticipated to receive ablation outside the PV ostia and CTI region
4. Previously diagnosed with persistent, longstanding AF and/or continuous AF > 7 days, or > 48 hrs terminated by cardioversion.
5. Any percutaneous coronary intervention (PCI) within the past 2 months.
6. Valve repair or replacement and presence of a prosthetic valve.
7. Any carotid stenting or endarterectomy.
8. Coronary artery bypass grafting (CABG), cardiac surgery (e.g. ventriculotomy, atriotomy), or valvular cardiac surgical or percutaneous procedure within the past 6 months.
9. Documented left atrium (LA) thrombus on baseline/pre-procedure imaging.
10. LA antero posterior diameter > 50 mm
11. Any PV with a diameter  $\geq$  26 mm
12. Left Ventricular Ejection Fraction (LVEF) < 40%.
13. Contraindication to anticoagulation (e.g. heparin).
14. History of blood clotting or bleeding abnormalities.
15. Myocardial infarction within the past 2 months.
16. Documented thromboembolic event (including transient ischemic attack [TIA]) within the past 12 months.
17. Rheumatic Heart Disease.
18. Uncontrolled heart failure or New York Heart Association (NYHA) function class III or IV.
19. Awaiting cardiac transplantation or other cardiac surgery within the next 12 months.
20. Unstable angina.
21. Acute illness or active systemic infection or sepsis.
22. Diagnosed atrial myxoma or interatrial baffle or patch.
23. Presence of implanted pacemaker or, implantable cardioverter defibrillator (ICD), or tissue-embedded, iron-containing metal fragments.
24. Significant pulmonary disease, (e.g. restrictive pulmonary disease, constrictive or chronic obstructive pulmonary disease) or any other disease or malfunction of the lungs or respiratory system that produces chronic symptoms.
25. Significant congenital anomaly or medical problem that, in the opinion of the investigator, would preclude enrollment in this study.

26. Women who are pregnant (as evidenced by pregnancy test if pre-menopausal), lactating, or who are of child bearing age and plan on becoming pregnant during the course of the clinical investigation.
27. Enrollment in an investigational study evaluating another device, biologic, or drug.
28. Has known pulmonary vein stenosis.
29. Presence of intramural thrombus, tumor or other abnormality that precludes vascular access, or manipulation of the catheter.
30. Presence of an IVC filter
31. Presence of a condition that precludes vascular access.
32. Life expectancy or other disease processes likely to limit survival to less than 12 months.
33. Presenting contra-indication for the devices (e.g. TTE, CT, Holter, etc.) used in the study, as indicated in the respective instructions for use.
34. Categorized as a vulnerable population and requires special treatment with respect to safeguards of well-being

Additional exclusion criteria for Neurological Assessment Evaluable (NAE) subjects:

35. Contraindication to use of contrast agents for MRI such as advanced renal disease, etc. (at PI discretion)
36. Presence of iron-containing metal fragments in the body
37. Unresolved pre-existing neurological deficit.

## 4.3 Participant Withdrawal or Termination

### 4.3.1 Reasons for Withdrawal or Termination

Participants are free to withdraw from participation in the study at any time upon request without penalty or loss of benefits to which they may otherwise be entitled. Participants will be informed prior to study entry that they are free to withdraw from the study at any time and for any reason without prejudice to their future medical care by a physician or the institution.

An investigator may terminate a subject's participation in the study if:

- Any clinical adverse event (AE), laboratory abnormality, or other medical condition or situation occurs such that continued participation in the study would not be in the best interest of the participant
- Withdrawal is in the subjects' best interest
- The participant no longer meets eligibility criteria or meets an exclusion criterion (either newly developed or not previously recognized) that precludes further study participation.
- Subject withdraws consent
- Subject is lost to follow up

Every subject should be encouraged to remain in the study until they have completed the protocol required follow-up period.

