### 4.3.2 Handling of Participant Withdrawals or Termination

If a subject is removed or withdraws from the study, the date and reason for withdrawal will be recorded on the appropriate electronic case report form (eCRF). If the subject is withdrawn due to an adverse event (AE) or serious adverse event (SAE), the Investigator should follow the subject until the AE/SAE has resolved or is considered stable.

If a subject is unable to return for an office/clinic visit or cannot be contacted by telephone, 3 separate telephone calls should be made to obtain subject related safety information. All attempts should be documented in the source documents. If the subject does not respond to the 3 telephone calls, then the investigator must send a certified letter to the subject. If the subject does not respond to the letter, then the subject will be considered “lost to follow-up” for the study.

Subjects who have signed the ICF, but are later found not to be eligible PRIOR to insertion of the study catheter can be replaced. Replacement subjects will be recruited and enrolled following the same procedures as non-replacement subjects.

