## 4.4 Subject Enrollment Disposition

- **Enrolled Subjects:** Patients who sign the informed consent form.
- **Evaluable Subjects:** All enrolled subjects who have the study catheter inserted.
- **Excluded Subjects:** Subjects who are enrolled but never undergo insertion of the study catheter. Excluded subjects will only be followed between ICF signature and exclusion for event reporting.
- **Roll-In Subjects:** Enrolled Subjects who have the study catheter inserted and RF delivered during the roll-In phase of the ablating investigator. These subjects will not be included in the main study analyses and will be analyzed separately.
- **Discontinued Subjects:** Enrolled subjects who have the study catheter inserted but do not undergo ablation (i.e., no RF energy is delivered with the study catheter). Discontinued subjects will remain in follow-up for 30 days.
- **Lost to Follow-up Subjects:** Evaluable subjects of which contact is lost after most recent visit (despite 3 documented attempts to contact the subject).
- **Withdrawn / Early Termination Subjects:** Subjects who withdraw consent for study participation or are withdrawn by the investigator, are terminated from the study prior to completion of all follow-up visits.
- **Completed Subjects:** Enrolled subjects who have not been excluded, discontinued, withdrawn, terminated early, or lost-to-follow-up from the study prior to the final study visit.

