Stroke/Cerebrovascular Accident (CVA)	
Diagnosis:
 
 
-Rapid onset of a focal or global neurological deficit with at least one of the following: change in level of consciousness, hemiplegia, hemiparesis, numbness or sensory loss affecting one side of the body, dysphasia or aphasia, hemianopia, amaurosis fugax, or other neurological signs or symptoms consistent with stroke.
 
-Duration of a focal or global neurological deficit <math>\geq 24</math> h; or <math>< 24</math> h, if therapeutic intervention(s) were performed (e.g. thrombolytic therapy or intracranial angioplasty); OR available neuroimaging documents a new hemorrhage or infarct; or the neurological deficit results in death.
 
-No other readily identifiable non-stroke cause for the clinical presentation (e.g., brain tumor, trauma, infection, hypoglycemia, peripheral lesion, pharmacological influences).†
 
-Confirmation of the diagnosis by at least one of the following: Neurology or neurosurgical specialist; Neuroimaging procedure (MR or CT scan or cerebral angiography); Lumbar puncture (i.e., spinal fluid analysis diagnostic of intracranial hemorrhage)
 
 
Definition:
 
Stroke: (diagnosis as above, preferably with positive neuroimaging study)
 
 
Minor—Modified Rankin score <math>< 2</math> at 30 and 90 days††
 
Major—Modified Rankin score <math>\geq 2</math> at 30 and 90 days
 

Transient Ischemic Attack	
New focal neurological deficit with rapid symptom resolution (usually 1 to 2 h), always within 24h; neuroimaging without tissue injury.

Phrenic Nerve Paralysis	
Absent phrenic nerve function as assessed by a sniff test, associated with symptoms of dyspnea and orthopnea (diagnosed by chest x-ray). A phrenic nerve paralysis is considered to be permanent when it is documented to be present 12 months or longer following ablation. Under this protocol, diaphragmatic paralysis/phrenic nerve palsy will be considered a Primary AE if specified symptoms have not improved at the 3- month visit

Primary Adverse Event	Description / Criteria
Pulmonary Vein Stenosis*	A reduction of the diameter of a PV. Severe PV stenosis ( $\geq 70\%$ reduction in the diameter of the PV) will be considered a primary adverse event and major complication of AF ablation.

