11.4.4 Handling of Missing Data

Interim Analysis:

At the time of each interim analysis, some subjects will not have completed the full 30-day follow-up for their safety evaluation. The number of failures for the primary safety endpoint in subjects with incomplete information will be assumed to follow a beta-binomial distribution. The predicted number of failures for the primary safety endpoint will be estimated from these beta-binomial distributions for estimating the predictive probability of success for the safety endpoint.

Final Analysis:

The reasons for missingness, if available, will be listed for subjects with missing data. Patients with missing effectiveness data will be excluded from the primary effectiveness analysis.

Subjects without full follow-up required per protocol for the safety endpoint assessment will be excluded in the primary analysis unless they have experienced a PAE. Sensitivity analyses for missing data will be performed to assess the impact of missing values on the primary safety outcome and are described in the section 11.4.5.

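### Protocol 4.3.1 lets the investigator end participation on a newly met exclusion criterion even after ablation, so late safety outcomes and, above all, rhythm outcomes can be lost for reasons linked to the outcome

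*Protocol*

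**What the plan says.** Protocol 4.3.1 lists the grounds on which an investigator may terminate participation. The third is: "The participant no longer meets eligibility criteria or meets an exclusion criterion (either newly developed or not previously recognized) that precludes further study participation". No time limit is attached. Protocol 4.4 gives the consequence: subjects who "are withdrawn by the investigator, are terminated from the study prior to completion of all follow-up visits".

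The protocol does draw a line at catheter insertion, but only for replacement: 4.3.2 says that subjects who "are later found not to be eligible PRIOR to insertion of the study catheter can be replaced".

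Several criteria in Protocol 4.2 describe states that can arise after ablation:
- criterion 4, continuous AF beyond 7 days;
- criterion 15, myocardial infarction;
- criterion 16, "Documented thromboembolic event (including transient ischemic attack [TIA]) within the past 12 months";
- criterion 18, NYHA class III or IV;
- criterion 23, an implanted pacemaker;
- criterion 28, "Has known pulmonary vein stenosis".

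Parts of the primary safety endpoint are settled late. Related death, PV stenosis and atrio-esophageal fistula count to day 90 (SAP 6.1.1). Phrenic nerve palsy "will be considered a Primary AE if specified symptoms have not improved at the 3- month visit" (Protocol Table 9.1.3-A).

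For primary safety, SAP 11.4.4 states: "Subjects without full follow-up required per protocol for the safety endpoint assessment will be excluded in the primary analysis unless they have experienced a PAE". For secondary endpoints, SAP 11.5 leaves out subjects with missing outcomes, and SAP 11.5.2.1 censors subjects with short follow-up and no failure at their last observation in the Kaplan-Meier analysis.

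**The concern.** Eligibility criteria protect a subject before treatment. Here the device is used once, and what follows is mainly observation. If the criteria stay in force after treatment, a complication or a relapse can itself become the reason for ending observation. The loss then depends on the outcome, and the decision rests with an unblinded investigator in a single-arm study.

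Two sets of results are at stake. For primary safety, a subject who leaves before day 90 or the 3-month visit without a PAE drops out of the primary analysis. For rhythm, a subject with continuous AF beyond 7 days in the first 90 days meets the wording of criterion 4. If participation ends then, the outcomes from day 91 on are never observed. The subject is excluded or censored, although the chance of later failure is probably higher than average.

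**Working it through.** **1. Which outcomes are exposed.** Each outcome is set against the time it is fixed and the safeguards that apply.

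| Outcome | Fixed when | Safeguard | Exposed? |
|---|---|---|---|
| Acute procedural success | At the procedure | Not needed | No |
| PAE that has already occurred | Before withdrawal | Counted (SAP 11.4.2, 11.4.4) | No |
| Related death, fistula, stenosis after day 7 | To day 90 | Known AEs followed (Protocol 4.3.2, 9.3); tipping point (SAP 11.4.5) | Partly |
| Phrenic palsy | 3-month visit | Same | Partly |
| Freedom from AF/AT/AFL | Day 91-180 and 91-365 | None: AF recurrence is not an AE (Protocol 9.1.1) | Yes |

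The safety rows are only partly exposed because AE follow-up attaches to the known event and runs until it is resolved or stable. It does not require the remaining endpoint visits. A palsy judged stable at 6 weeks, or a different late event, could still be missed.

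For rhythm, SAP 11.5.2.1 adds an analysis in the Safety Population on a wider set of subjects. It specifies no sensitivity analysis for missing rhythm outcomes.

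**2. The plan's own figure.** Inputs: safety goal 15%, exact one-sided 5% test (SAP 11.4.2), maximum N = 230 and anticipated rate of at most 9.5% (SAP Appendix, section 2). The largest k with P(X ≤ k | N, 0.15) ≤ 0.05 is 25 at N = 230. Then P(X ≤ 25 | 230, 0.15) = 0.044 and P(X ≤ 25 | 230, 0.095) = 0.797. This agrees with the stated 80% fixed-design power after rounding.

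**3. One lost event at the boundary.** The same rule allows at most 6/80, 12/130, 18/180 and 25/230. The one-sided 95% Clopper-Pearson upper bound is the 0.95 quantile of Beta(k+1, N−k):
- 7/80: 15.8%, fails; 6/79: 14.4%, passes.
- 26/230: 15.3%, fails; 25/229: 14.9%, passes.

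One lost event likewise turns failure into success at N = 130 (13/130 to 12/129) and N = 180 (19/180 to 18/179).

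**4. The opposite direction.** 25/230 passes (14.85%). If three subjects without an event are removed, 25/227 fails (15.04%). Removal can therefore also hurt the device.

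**5. Type I error, upper-end illustration.** The documents give no removal rate. Assume a fraction w of event subjects is lost from numerator and denominator, with fixed N = 230 and a true rate of 15%. The number lost is D ~ Bin(230, 0.15w), and each remaining subject has event probability 0.15(1−w)/(1−0.15w). Summing over D:

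| w | Type I error |
|---|---|
| 0 | 0.044 |
| 2% | 0.056 |
| 5% | 0.074 |
| 10% | 0.113 |

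Only late-determined PAEs can be lost, so w as a share of all events should be small.

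**6. Rhythm endpoints.** Assume true 12-month freedom of 75%, and that a fraction r of subjects is removed, all of whom would have failed. Reported freedom = 0.75/(1−r):
- r = 2%: 0.75/0.98 = 76.5%
- r = 5%: 0.75/0.95 = 78.9%

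**The case against.** The strongest case against is that the safeguards are substantial. Subjects withdrawn for an AE are followed until it is resolved or stable, and all AEs are to be followed to resolution. Subjects are to be encouraged to stay. A repeat ablation does not reset the visit schedule. The tipping-point analysis works through all possible outcomes for missing safety data. The rule is discretionary and applies only where the criterion precludes further participation. The plan assumes negligible attrition, and the rhythm endpoints are descriptive with no hypothesis. All of this stands. It narrows the point to late safety components and rhythm, but does not close the gap there: the qualifier is undefined, and the tipping-point analysis does not replace the primary result or reach the rhythm endpoints.

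A reader might infer more than the documents support:
- *The PAE rate can only look better.* Step 4 of the working shows the reverse can happen.
- *Every treated subject qualifies for removal, having now had an AF ablation (criterion 2).* The qualifier, and continued follow-up after repeat ablation, speak against this.
- *Post-procedure LA thrombus is a trigger.* Criterion 9 is tied to baseline or pre-procedure imaging.
- *No criterion could ever hinder follow-up.* Follow-up includes TTM, Holter and, for some subjects, CT/MRA or cerebral MRI, and criterion 33 concerns contraindications to study devices.
- *Mild stenosis would often be found early and used this way.* Post-ablation CT/MRA is planned only at 3 months, in symptomatic subjects.

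Finally, the first two bullets of 4.3.1 (a medical condition, or the subject's best interest) could end participation for the same subjects. Changing the third bullet alone would be incomplete.

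**Conclusion.** The concern holds in a limited form. The text permits outcome-related loss of treated subjects, and the SAP then excludes or censors them. The clearest exposure is in the 6- and 12-month rhythm endpoints. Primary safety is exposed only through its late-determined components. Acute effectiveness is not affected.

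The likely direction is favourable to the device, without certainty. The size cannot be derived from the documents: the 75% freedom, the 2% to 5% removals and the values of w are assumptions, and the boundary examples need the count to sit exactly at the limit. They show that a single lost safety event can decide the result, and that a few removals can move the rhythm rates by about 1.5 to 4 percentage points. They do not show that this will happen. The change is worth making because it is cheap and removes a stated route to informative loss.

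**What to change.** Amend Protocol 4.3.1 in three steps:
1. Limit the eligibility bullet to the time before study-catheter insertion.
2. State that after insertion, an exclusion criterion newly met or newly recognized is not in itself a reason to end follow-up. The subject stays in the scheduled safety and rhythm follow-up, leaving out any single assessment that is contraindicated, unless consent is withdrawn or one of the first two bullets applies.
3. Where one of those two bullets is used, still collect, with the subject's consent, at least PAE status through day 90 and the 3-month visit, and any available rhythm outcomes.

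The cost is a short protocol amendment with no new visits. The downside is that a few subjects who might have left early remain in visits already on the schedule.
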